In a second experiment, an attempt was made to reproduce the posture of a non-rigid, female mannequin placed on the couch of a CT scanner. The first setup was done using only setup photos and room lasers, typically the only tools available for this type of “verification CT scan”.⁴ The second setup was performed using MixRT. In both cases, CT scans of the mannequin were acquired and registered with the initial, simulation CT scan using the torso as the area of focus. With the torso aligned in both registrations, the difference in arm position provides a way to assess the correctness of the overall posture. As seen in Figure 3, the MixRT setup outperforms the standard setup which showed a difference in arm position of 2 cm and further required a roll of 6-7 degrees in order to align the torso. In a real treatment scenario, this misalignment would require further manual correction, increasing the utilization of IGRT, overall setup time, and with no guarantee of a result matching that provided by MixRT. As previously noted, sub-optimal setups are often accepted, even with IGRT, due to the pressure to stay on schedule, minimize patient discomfort that can occur with prolonged time on the treatment couch, and the limitations of current methods. Thus, MixRT, with its ability to naturally guide both patient alignment and adjustment in real-time, provides a mechanism for increasing the overall accuracy of the treatment delivery and associated outcomes.

Figure 3. Preliminary accuracy of MixRT for non-rigid alignment demonstrating the elimination of roll and accurate arm placement compared to standard alignment methods. Left-to-right (axial, sagittal, coronal views).

5.) Specific Aims:

Perform a pilot study to assess the feasibility of MixRT. Feasibility will be based on the accuracy, overall setup time, and amount of IGRT needed when utilizing MixRT for patient setup in breast RT and in comparison, with current methods. Comparisons will be made between MixRT and 3-point alignment for photon treatment, and MixRT/IGRT versus IGRT alone for pencil beam scanning proton treatment. This data will establish viability and provide the framework for larger comparative effectiveness research studies and eventual FDA clearance.

6.) Research Plan:

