- **Describe the inclusion and exclusion criteria for this project:** This study will target adult patients who are planning to undergo photon or proton radiation therapy at UFHPTI for treatment of the breast or chest wall. As this type of treatment is rare in men, the study will focus on female patients only.
- **Provide a thorough step-by-step description of what you intend to do throughout the course of the study in a logical and sequential format:**

Hologram creation

For all patients included in this study, we will create holograms based on the external body contour derived from their planning CT dataset. This contour is routinely segmented during treatment planning; thus, we will only need to access the existing contour located in the software system MimVista and export it to our software system. We will also access patient setup photos located in a clinical file system and export these to our application.

Mixed-reality guided patient setup

At UFHPTI, we treat breast/chest wall patients using various modalities and techniques. In all cases, patient setup begins with a 3-point alignment. The additional use of IGRT depends on modality, approach, and patient-specific variables. Most patients treated with 3D conformal photon therapy (3DCRT) receive only weekly IGRT, including kV orthogonal and MV portal imaging. The 3-point alignment, thus, represents the standard setup for the majority of treatment, both here and across the nation, as 3DCRT is the most common technique for breast RT. As such, one of our primary aims is to pilot the clinical implementation of MixRT with the goal of accuracy similar to or better than a traditional breast setup involving 3-point alignment (5mm tolerance).

We will recruit 12 patients scheduled to receive whole breast or chest wall RT using a supine, 3DCRT or IMRT approach. All patients will be consented for a study comparing the accuracy of MixRT with a traditional 3-point alignment as quantified using CBCT. To control for setup variation which typically decreases after the first few treatment fractions, we will stratify patients into two groups using an alternating method. In the first group, the therapists will position the patient using 3-point alignment during fractions 1-5 (5 total), then using MixRT for fractions 6-10 (note:

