16 fractions is a common course of breast RT). For the second group, we will reverse the order, using MixRT for fractions 1-5 and 3-point alignment for fractions 6-10. In this way, each patient will serve as their own control. In all cases, patient alignment will be verified using CBCT which will be registered to the simulation CT by the treatment therapists using the standard clinical workflow. The magnitude of the resulting shift will be recorded. If further adjustment is necessary, the number of repeated CBCTs will be recorded along with the shift magnitude. All registrations will be reviewed by a board-certified radiation oncologist (one of the co-investigators) who will qualitatively assess the accuracy of the setup while blinded to the setup method. The process for mixed-reality alignment is noted below:

1. Identify the patient and initialize their hologram by detecting a QR-coded cube attached to the treatment device.
2. Setup the patient according to their setup photos, related immobilization devices (typically only an inclined breast board), and 3-point alignment. Further match the patient to their hologram as viewed through the HoloLens 2 device.
3. Utilize IGRT to verify proper alignment per protocol or departmental standards.
4. Make corrections as needed based on IGRT.
5. Repeat steps 1-3 if necessary.

For patients receiving proton therapy, setup typically includes routine CBCT, the challenges of which were previously discussed for non-rigid alignment including prolonged setup time and increased imaging dose. The primary goal of this sub-aim is thus to show that MixRT can reduce setup time and the amount of imaging dose in cases requiring CBCT alignment. To evaluate this, we will recruit an additional 12 patients scheduled to receive RT using a supine, pencil-beam scanning approach. As with 3DCRT/IMRT approach, we will divide patients into two groups using an alternating method and alternate the setup approach between fractions 1-5 and 6-10, reversing the order between the two groups. Setup time will be tracked from the moment the patient lies on the treatment couch to when the final position is confirmed by the therapist prior to treatment. Patient alignment will be verified/quantified in a similar manner as noted above.

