A window period of 2 additional fractions is permissible for the collection of study data. This window period is provided to allow a patient to remain on study through her 12th fraction of treatment if the patient is not able to receive the study intervention during one to two of her first 10 fractions.

To summarize, we intend to enroll 12 patients receiving either 3DCRT or IMRT and 12 patients receiving proton therapy. Within each modality, patients will be randomized into two groups using an alternating method. The order in which MixRT will be utilized will be reversed between the groups. The measured data will include registration accuracy (6 DoF shifts), setup time, and number of CBCT's utilized. Registration accuracy will be quantified using the image registration module that is used as part of the IGRT process. Setup time will be quantified using a stopwatch.

The number of CBCT's will be quantified via counting the number that are used during the setup process. Patients receiving photon IMRT receive daily CBCT as part of the standard of care. Thus, this investigation would likely not introduce additional imaging dose for these patients. For proton therapy CBCT is used weekly, and for 3DCRT it is not routinely used. Thus, this investigation would represent a marginal increase in the utilization of CBCT for these patients, up to 10 extra CBCT's nominally.

Setup during Verification CT

Radiotherapy patients at UFHPTI often receive repeat CT scans (verification scans) at periodic timepoints during the course of treatment to assess for anthropomorphic changes that could have dosimetric effect. Reproducing the posture from the initial CT simulation is critically important yet difficult to achieve due to the lack of real-time feedback. For patients who receive a verification CT (likely all proton patients), we will implement holographic alignment during this process and assess its accuracy in comparison to CT acquisition without the aid of holographic alignment. The procedure will be as follows:

1. Identify enrolled patients scheduled to receive a verification CT scan.
2. Setup patient without the aid of holographic alignment (standard method).
3. Acquire verification CT scan.
4. Dismantle the setup.
5. Utilize holographic alignment to correct patient posture. This involves a therapist wearing the HoloLens 2 device and viewing the patient's reference hologram overlaid the patient. The therapist will manually adjust the patient to match the hologram.

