- **Briefly outline the data analyses that are proposed and who will do the analysis:** Mean estimates and associated 95% confidence intervals will be attained for registration error and registration time for the mixed reality and standard of care methods and the paired difference of the two techniques. We will assess feasibility using a paired T-test. The hypothesis is that the mean paired differences across all measures of registration error and registration time are not significantly different than 3 mm and 5 minutes, respectively. The number of CBCTs collected as part of the registration process will be assessed subjectively since count data are not truly continuous. This analysis will be carried out by the study investigator and study statistician.
- **Describe your plan for conducting interim analysis. What stopping rules are in place?** N/A.

8.) Data Safety and Monitoring Plan:

- **Is there a Data Safety Monitoring Board (DSMB) or an oversight committee for this research project?** The UF Data Integrity & Safety Committee will provide oversight through annual monitoring.

- **Describe your plans for monitoring study conduct and subject safety:** The Principal Investigator will be responsible for monitoring.
- **Provide Information about the DSMB or committee including who is on the committee, how frequently will the committee meet, and when will you get information from the committee:** N/A

9.) Possible Discomforts and Risks:

- **Identify all discomforts and risks (physical, psychological, social, and/or economic) study participants may encounter, listing more common risks first and less common risks separately:** Based on prior study utilizing anthropomorphic phantoms, we anticipate that our patient alignment system will ultimately reduce setup time and the number of X-ray images used for alignment. We have yet to try this with patients, however, and there is a risk that it could marginally increase setup time, at least during the initial implementation.

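### Section 7 does not say whether a pair in the paired t-test is a patient or a fraction, and has no term for the order of methods, so its intervals may be too narrow or too wide

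*Combined protocol and SAP*

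**What the plan says.** The design is in section 6, under Mixed-reality guided patient setup. For the photon cohort: "In the first group, the therapists will position the patient using 3-point alignment during fractions 1-5 (5 total), then using MixRT for fractions 6-10". The second group reverses this, "using MixRT for fractions 1-5 and 3-point alignment for fractions 6-10". The proton cohort follows the same block scheme, with 12 patients per modality. The stated reason for reversing the order is that setup variation usually falls after the first few fractions. Section 6 describes each patient as her own control. Its item on the experimental control adds that the control is her set of fractions without the hologram.

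The analysis is in section 7: "Mean estimates and associated 95% confidence intervals will be attained for registration error and registration time", for each method and for the paired difference. The test is named in one sentence: "We will assess feasibility using a paired T-test". What it is to examine is whether "the mean paired differences across all measures of registration error and registration time are not significantly different" from reference values of 3 mm for error and 5 minutes for time. Nothing more is said about pairs, averaging within a patient, clustering or order.

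**The concern.** The data have two levels, fractions within patients, and a planned order effect. The analysis text addresses neither.

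Five values from one patient are not five independent pieces of information. For the paired difference, a patient's general level cancels, and what remains shared is her own response to the method. For the separate per-method means her general level does not cancel, so those intervals are the more exposed part. If fractions are pooled as independent, both kinds of interval are too narrow whenever the shared part varies between patients.

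Fraction-level pairing is also undefined. Fraction 1 in one block has no natural partner among fractions 6 to 10. Blocks may be unequal too, because section 6 allows data collection to slip to fraction 12 and section 9 allows hologram use to be stopped for an individual.

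Section 6 treats registration error and registration time as primary endpoints, and section 7 gives the only planned inference on them. The aims say the data will "provide the framework for larger comparative effectiveness research studies". Sizing such a study needs between-patient and fraction-to-fraction SDs, which section 7 does not plan to report.

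**Working it through.** There is no planned figure to reproduce. The documents give no SD, correlation or power, and section 7 says the sample size was chosen for practicality.

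**From the documents (section 6).** 12 patients per cohort and m = 5 fractions per method, so 12 × 5 = 60 fraction pairs per cohort. Two order groups, taken as 6 + 6.

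**Assumed.** Per-fraction SD 2 mm for each method. SD of the true method effect between patients (τ) 0 to 2 mm. Mean shift between blocks (π) 0, 1 or 2 mm. Two-sided 5%, from the 95% intervals.

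**Analysis A: 60 pairs treated as independent (59 df).** Variance of one fraction difference = τ² + 2 × 2² = τ² + 8. The within-patient correlation is ρ = τ²/(τ² + 8), and the SE is too small by √(1 + 4ρ).

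- τ = 1: ρ = 1/9 = 0.11, factor √1.44 = 1.20
- τ = 1.5: ρ = 2.25/10.25 = 0.22, factor √1.88 = 1.37
- τ = 2: ρ = 4/12 = 0.33, factor √2.33 = 1.53

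**Analysis B: 12 patient differences, no order term (11 df).** Variance of one patient difference = τ² + 8/5.

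Simulated coverage and mean half-width with π = 0:

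| τ (mm) | A: coverage | A: half-width | B: coverage | B: half-width |
|---|---|---|---|---|
| 0 | 95% | 0.73 | 95% | 0.79 |
| 1 | 90% | 0.77 | 95% | 1.00 |
| 1.5 | 85% | 0.82 | 95% | 1.22 |
| 2 | 80% | 0.88 | 95% | 1.47 |

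Hand check at τ = 1. A: 2.001 × √(9/60) = 0.775. B: 2.201 × √(2.6/12) = 1.02. The simulated means are slightly lower because a sample SD averages a little below the true SD.

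**Per-method means, 60 values treated as independent.** With an assumed intraclass correlation of 0.1 / 0.3 / 0.5, the design effect 1 + 4 × ICC is 1.4 / 2.2 / 3.0. The SE is too small by 1.18 / 1.48 / 1.73, and coverage is about 90% / 81% / 73%.

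**Effect of order.** A block shift π enters the differences as +π in one group and −π in the other. With 6 + 6 it cancels from the mean but adds π² × 12/11 to the variance estimated from 12 differences. At τ = 1:

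- π = 1, B: variance 2.6 + 1.09 = 3.69, so 2.201 × √(3.69/12) = 1.22 (simulated mean 1.19, coverage 98%)
- π = 2, B: variance 2.6 + 4.36 = 6.96, so 2.201 × √(6.96/12) = 1.68 (simulated mean 1.65, coverage above 99%)
- Order-adjusted, 10 df, any π: 2.228 × √(2.6/12) = 1.04 (simulated mean 1.01, coverage 95%)

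The same shift moves A from 90% coverage at π = 0 to 91% at 1 mm and 95% at 2 mm.

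**The case against.** The strongest reply is that the documents never say n = 60 or that a pair is a fraction. Section 6 lists the data as follows: "The measured data will include registration accuracy (6 DoF shifts), setup time, and number of CBCT's utilized". The phrase in section 7 about all measures may therefore mean kinds of outcome rather than every fraction. The only pair the documents describe is the patient: she is her own control, and her control is a whole set of fractions. A paired t-test on patient means is valid and needs no patient term. This stands. A reader might infer that a 60-pair analysis is planned and that its intervals will be too narrow, but the text supports only that this analysis is permitted. The patient-level reading also does not settle the matter, because section 7 does not carry it into the test or the per-method intervals, and it leaves order unmodelled.

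A reader might also infer that early-fraction effects make the intervals narrower still, since they move all of a patient's differences together. The reversed order rules that out. With balanced groups the shift cancels from the mean and inflates the estimated variance, so it widens the interval.

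Two limits on size are fair. Every SD, correlation and shift above is assumed, and with no patient variation there is no narrowing. The change in half-width is also modest beside the 3 mm reference value, in a study that calls itself underpowered. That lowers the urgency, but low power does not excuse intervals with the wrong coverage.

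**Conclusion.** The concern holds as an undefined unit of analysis combined with a missing order term. It does not show that invalid intervals are planned. The stated paired t-test can be miscalibrated on either reading:

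- **Fractions as pairs:** too narrow if patients vary. Coverage is about 80 to 90% for the difference (assumed τ of 1 to 2 mm) and about 73 to 90% for per-method means (assumed intraclass correlation 0.1 to 0.5). A block shift partly offsets the loss for the difference.
- **Patients as pairs, no order term:** too wide if the mean shifts between blocks. The half-width is 1.19 to 1.65 mm against 1.01 mm adjusted, for an assumed 1 to 2 mm shift at τ = 1 mm.

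The protocol expects setup variation to fall over early fractions. It does not say that the mean shifts. A fall in spread would lower the mean if error is analysed as a magnitude, but need not do so for signed shifts, so the second item depends on how error is defined.

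This should be fixed before analysis. It does not undermine the design, and no planned sample size or power figure changes.

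**What to change.** In section 7, state that the patient is the unit of analysis. For each cohort and endpoint, use one of these:

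1. Average the available fractions per method within each patient, form one difference per patient, and estimate the method effect adjusted for order group (10 df with 12 patients).
2. Fit a linear mixed model to the fraction-level values, with method and block as fixed effects and patient and patient-by-method as random effects. This also handles unequal numbers of fractions.

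A t-test on the 12 differences without the order term (11 df) is not interchangeable with either. Build the per-method intervals on the same basis. Report the between-patient, patient-by-method and fraction-to-fraction SDs for the next study.

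The cost is a few sentences. Intervals may be wider than a 60-pair analysis would show, and one degree of freedom goes to order. No new patients, imaging or data are needed.

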Surface-guided radiation therapy (SGRT) is a technique that complements IGRT in many respects. While IGRT excels at aligning internal anatomy, SGRT emphasizes the matching of external surfaces.⁵ In terms of setup, the strength of the technique is a real-time, 3D reconstruction of the patient surface, which allows for immediate correction of patient posture and alignment when compared to a reference body surface derived at the time of simulation. To accomplish this, SGRT systems utilize ceiling-mounted light emitters and optical cameras. The emitters project a known light pattern onto the patient's skin that is reflected and captured by the optical cameras; thereafter, the patient surface can be reconstructed in 3D and displayed on a conventional 2D monitor. Several studies have quantified the benefits of SGRT in comparison to a traditional 3-point setup (no IGRT) for patients with tumors of the breast, chest wall, and extremities.⁶⁻¹⁰ The largest improvements are seen when treating intact breasts, which present challenges based on the independent movement of the local anatomy and the deformability of the pendulous target. By reducing the initial shifts, the need for iterative adjustment is reduced. In one study, this translated to a decreased setup time from 11 to 6 minutes, indicating reduced radiographic imaging and, consequently, reduced imaging dose to the patient.¹¹ Reducing setup time also minimizes patient discomfort that can occur with prolonged time on the treatment couch.

While SGRT represents a favorable complement to IGRT, it is not without limitations. For the patient surface to be recognized, the ceiling-mounted components must remain unobstructed during the setup procedure and map only the skin surface that can receive and reflect the light pattern. This line-of-sight approach often means a limited FOV and an inability to track surfaces in contact with the couch or behind other anatomy. Obstruction is also a limiting issue for certain room designs when components of the RT delivery system can block the overhead cameras during portions of the setup process. Besides obstruction and FOV limitations, SGRT is not currently optimized for the ways in which therapists set up patients. Because the real-time surface is displayed on a computer

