Figure 2. System for patient alignment via hologram: A) Initial simulation CT scan, B) Creation of 3D object file from body contour, C) Development platform where patient isocenter is linked with virtual representation of physical marker, D) Physical marker attached to machine at pre-determined location linking patient isocenter with radiation isocenter; patient hologram (blue) is visualized through HoloLens v2 highlighting the mis-alignment of the mannequin (white), E) Physical mannequin adjusted to match the reference hologram, thus reproducing the required posture and registering the mannequin with the RT device.

Table 1. Preliminary accuracy of MixRT for rigid alignment.

	User 1	User 2	User 3	Mean	StDev
Shift (mm)	n = 5				
Vrt	0.8	0.6	1.5	1.0	0.8
Lng	1.1	1.3	1.2	1.2	0.7
Lat	2.0	1.8	2.4	2.1	1.5
RMS	2.4	2.6	3.3	2.8	1.4
Shift (°)	n = 15				
Rtn	0.4	0.7	0.7	0.6	0.6
Pitch	0.1	0.1	0.0	0.1	0.1
Roll	0.1	0.1	0.1	0.1	0.1

[figure not shown]
In preparation for this study, we have developed a preliminary application to enable MixRT and provide initial estimates of hologram stability, alignment accuracy, and user variability. In one experiment, three users were tasked with aligning a rigid anthropomorphic phantom with an RT device (linear accelerator) while wearing the HoloLens v2. Each user performed the alignment five times, and accuracy was quantified using IGRT.

For each user, all five measurements were completed within the same session. Between measurements, the setup was disassembled and reset. The results shown in Table 1 preliminary estimate an overall accuracy of 3 ± 1 mm. These results were consistent between all users across all sessions. Considering the preliminary nature of the study, these results

are extremely encouraging, achieving less than the 5 mm alignment tolerance for 3D photon treatments and approaching the 2 mm alignment tolerance for proton treatments.

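### Feasibility rests on a paired difference being not significantly different from 3 mm and 5 minutes, with no sign defined: this cannot show similarity, and imprecise data favour it

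*Combined protocol and SAP*

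**What the plan says.** Section 7 (Statistical Analysis) plans means and 95% confidence intervals for registration error and registration time under each method, and for "the paired difference of the two techniques". It then says "We will assess feasibility using a paired T-test", with the hypothesis that the "mean paired differences across all measures of registration error and registration time are not significantly different than 3 mm and 5 minutes, respectively". It gives no alpha level, sidedness, order of subtraction, source for the two figures, or rule that uses a confidence limit. CBCT counts are to be judged subjectively, so this is the only formal test of feasibility.

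The aims in section 6 have a direction. For photon patients, MixRT is piloted "with the goal of accuracy similar to or better than a traditional breast setup involving 3-point alignment (5mm tolerance"). For proton patients, "The primary goal of this sub-aim is thus to show that MixRT can reduce setup time and the amount of imaging dose".

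**The concern.** A non-significant test does not show that a difference equals the tested value; it shows only that the data could not exclude it. Small or noisy studies exclude less, so a hypothesis supported by non-significance is easier to satisfy with poorer data. This holds whenever the true difference is not exactly the reference value; at that value non-rejection stays at 95%.

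The tested value adds a second problem. The null is placed at 3 mm and 5 minutes rather than at zero, and the sign is open. The documents do not settle the direction:

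- **Time.** The 5-minute change cited in section 4 is a saving (surface guidance: "this translated to a decreased setup time from 11 to 6 minutes"), but section 9 warns that "there is a risk that it could marginally increase setup time" with MixRT.
- **Accuracy.** The 3 mm matches the phantom result in section 4 ("preliminary estimate an overall accuracy of 3 ± 1 mm"). That is an absolute error, not a difference between two methods.
- **Metric.** It is unclear what the registration-error measures are. They could be repeated measurements, the recorded shift magnitude, or all six degrees of freedom. Three of those six are rotations, to which a millimetre value cannot apply. Section 6 also lists surface-distance metrics for the verification CT.

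At stake is the direction of the feasibility conclusion, which is meant to support larger studies and eventual FDA clearance.

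**Working it through.** The plan has no power or sample-size figure to reproduce, so the check computes how the stated hypothesis behaves.

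**Inputs from the documents:** 12 photon and 12 proton patients (section 6); reference values 3 mm and 5 minutes, paired t-test (section 7).

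**Assumptions:** one paired difference per patient; analysis by cohort (n = 12); two-sided 5%, to match the 95% intervals; SD of the paired difference 2 to 6 mm for accuracy and 5 to 10 minutes for time. The documents give no SD for patients.

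**Formula.** For true mean difference μ and reference value θ, the hypothesis is met when |T| < t(0.975, n−1). T is noncentral t with n−1 degrees of freedom and noncentrality (μ − θ)/(SD/√n). For n = 12 the critical value is 2.201.

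**Accuracy, MixRT truly equal to control (μ = 0, θ = 3 mm).** Example: SD 3 mm, n = 12 gives noncentrality −3/(3/√12) = −3.46 and a non-rejection probability of 0.117.

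| n | SD 2 mm | SD 3 mm | SD 4 mm | SD 6 mm |
|---|---|---|---|---|
| 6 | 17% | 49% | 68% | 83% |
| 12 | 0.3% | 11.7% | 34% | 65% |
| 24 | 0% | 0.3% | 6% | 35% |

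Agreement with the hypothesis rises as SD rises and as n falls. In a simulation of 400,000 trials at n = 12, when an equal MixRT was not rejected at 3 mm, the same 95% interval also contained zero in about 86%, 93% and 96% of cases at SD 3, 4 and 6 mm. Most such results are compatible with both values.

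**Accuracy, effect of the sign (n = 12).** With MixRT minus control:

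- A device 3 mm worse has μ − θ = 0 and is not rejected 95% of the time at any SD.
- A device 3 mm better has μ − θ = −6 mm and is not rejected 0.0%, 0.3% and 11.7% of the time at SD 3, 4 and 6 mm.

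With the reverse sign, the device 3 mm better sits on the null, and sufficiently precise data reject improvements larger than 3 mm. Under either sign a precise zero difference is rejected, although the photon aim would count it as success.

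**Proton time, read as a 5-minute saving (control minus MixRT, θ = 5, n = 12).**

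| True saving | Result | SD 5 min | SD 8 min | SD 10 min |
|---|---|---|---|---|
| 0 min | not rejected | 11.7% | 49% | 65% |
| 10 min | rejected | 88% | 51% | 35% |

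When a device with no saving is not rejected, the interval also contains zero in about 86%, 95% and 96% of cases. On this reading a zero difference may fairly count against MixRT, but non-rejection still does not demonstrate a saving.

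**The case against.** The strongest reply is that this is an admitted pilot with no formal power, and the test is not a gate. Section 6 says error, time and imaging are to be read together, and a blinded radiation oncologist also reviews the setups. The plan attaches no action to the test result, and the 95% intervals already planned carry the information needed. All of that is true. It excuses an inconclusive result, but not a criterion that low power makes easier to meet and that can point the opposite way to the interval beside it.

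Second, the sentence could be a loosely worded null at 3 mm and 5 minutes, with rejection on the favourable side as success. For accuracy, with MixRT minus control, that would amount to a non-inferiority test with a 3 mm margin. This is the less natural reading, and it would still need a stated sign, direction and margin.

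Third, the percentages depend on assumed SDs. The only comparable spread in the documents is the phantom root-mean-square SD of 1.4 mm (section 4, Table 1), which is not an SD of paired differences in patients. At that value, with n = 12, an equal MixRT is not rejected about 0.0% of the time, so the problem of imprecision could be small. A precise zero would then contradict the hypothesis almost every time. The larger time SDs are wide against setup times of 11 and 6 minutes. Pooling the cohorts (n = 24) would lower the rates, as the table shows. These points limit the size of the effect and leave the mechanism as it is.

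**Conclusion.** The concern holds and the text should be corrected before the data are analysed. Non-rejection of 3 mm or 5 minutes cannot support feasibility, the direction of the difference is undefined, and for photon accuracy the stated hypothesis conflicts with the study's own aim under either sign. With MixRT minus control, a device 3 mm worse agrees with it 95% of the time whatever the SD. The other rates illustrate the mechanism under assumed SDs, patient-level pairs, a two-sided 5% level and 12 patients per cohort; they do not predict this trial's results. The planned estimates and intervals remain sound.

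**What to change.** 1. Define the paired difference as MixRT minus control.
2. Delete the hypothesis of no significant difference from 3 mm and 5 minutes.
3. Name the millimetre metric to be analysed, for example the shift magnitude already recorded, and report rotations separately in degrees.
4. Base the accuracy conclusion on the planned 95% interval, by cohort, in one of two ways:
   - (a) Claim similar or better accuracy only if the upper limit lies below a margin that the sponsor prespecifies and justifies.
   - (b) If no margin can be justified, report the signed estimate and interval with no pass/fail claim.
5. For proton setup time, report the interval against zero.

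The chance of meeting option (a) at n = 12 when MixRT equals control is P(T < −2.201) with noncentrality −margin/(SD/√12):

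| Illustrative margin | SD 2 mm | SD 3 mm | SD 4 mm | SD 6 mm |
|---|---|---|---|---|
| 3 mm | 99.7% | 88% | 66% | 35% |
| 2 mm | 88% | 56% | 35% | 18% |

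Imprecision now makes success harder, as it should. For proton time, the upper limit falls below zero for a true 5-minute saving 88% and 51% of the time at SD 5 and 8 minutes, and for a 2-minute saving 24% and 12%.

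The cost is a change of wording; option (a) also needs a written justification of the margin, which the documents do not contain. No extra patients or data are needed. The drawback is that the result may be inconclusive if the SD is large. The interval half-width, 2.201 × SD/√12, is 1.9, 2.5 and 3.8 mm at SD 3, 4 and 6 mm, and 3.2 and 5.1 minutes at SD 5 and 8 minutes.
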